	
3. Analyze Select Outcomes of Interest:
 
• Time to Treatment Failure (TTF) - the time from therapy start to treatment discontinuation or therapy change (next line of therapy – switch or augment), end of enrollment, or death;• Treatment Interruption – those with gaps in treatment greater than allowable gap but who restart the same medication with no indication of switching or augmentation;• Health Care Costs (inpatient, outpatient, pharmacy, other);• Health Care Utilization (inpatient hospitalizations, ER, outpatient visits);• Survival Time and Landmark Survival. Mean/median survival time and % of population surviving 3, 6, and 12 months will be explored, although regimens are too new for extensive follow-up time. (Note: survival analysis will only be available in the Optum Clininformatics Database).
	
PPD [REDACTED], PharmD, MSc Director, PPD [REDACTED] [REDACTED] New York, NY 10017 Email: PPD [REDACTED]
 
PPD [REDACTED] Sr. Director, PPD [REDACTED] [REDACTED] Rockland, MA 02370 Email: PPD [REDACTED]
 
PPD [REDACTED], MD Title Address Email: PPD [REDACTED]
 
PPD [REDACTED] Executive Director, PPD [REDACTED] [REDACTED] New York, NY 10017 Email: PPD [REDACTED]

PFIZER CONFIDENTIAL

[REDACTED]

	PPD [REDACTED], MPH Director, PPD [REDACTED] New York, NY 10017 Email: PPD [REDACTED]
	PPD [REDACTED], MPH Manager, PPD [REDACTED] New York, NY 10017 Email: PPD [REDACTED]
	PPD [REDACTED] Intern, PPD PPD New York, NY 10017 Email: PPD [REDACTED]

PFIZER CONFIDENTIAL

[REDACTED]

TABLE OF CONTENTS

[figure not shown]
[figure not shown]
1. LIST OF ABBREVIATIONS.....	7
2. RESPONSIBLE PARTIES.....	9
3. AMENDMENTS AND UPDATES.....	10
4. RATIONALE AND BACKGROUND.....	10
5. RESEARCH QUESTION AND OBJECTIVES	11
6. RESEARCH METHODS	12
6.1. Study Design	12
6.2. Setting.....	17
6.2.1. Inclusion Criteria	17
6.2.2. Exclusion Criteria	18
6.3. Variables.....	19
6.3.1. Treatment Pattern Variables	19
6.3.2. Baseline Variables	21
6.3.3. Outcomes Variables.....	26
6.3.4. Cost and Utilization Variables.....	27
6.4. Data Sources.....	30
6.5. Study Size.....	33
6.6. Data Management	33
6.6.1. Record Retention	33
6.7. Data Analysis	34
6.8. Quality Control.....	35
6.9. Limitations of the Research Methods.....	35
6.10. Other Aspects	35
7. PROTECTION OF HUMAN SUBJECTS	35
7.1. Patient Information.....	35
7.2. Patient Consent.....	35
7.3. Institutional Review Board (IRB)/Independent Ethics Committee (IEC)	35

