5. RESEARCH QUESTION AND OBJECTIVES

The study aims to address the following key objectives among patient cohorts diagnosed with advanced/metastatic RCC:

Objective 1: Treatment patterns: Characterize first-line and subsequents lines of therapy. Treatment patterns will be summarized for the following therapy regimens:

- immuno-oncology (IO) monotherapy;
- IO+IO combo-therapy;
- IO+tyrosine kinase inhibitor (TKI) combo-therapy;
- TKI monotherapy;
- Other.

Objective 2: Analyze Cohorts of Interest: To describe patient demographics and clinical characteristics, and select outcomes of interest among the following first-line advanced RCC cohorts of interest:

- immuno-oncology (IO) monotherapy;
- IO+IO combo-therapy;
- IO+tyrosine kinase inhibitor (TKI) combo-therapy;
- TKI monotherapy;
- Other.

Objective 3: Analyze Select Outcomes of Interest:

- **Time to Treatment Failure (TTF)** - the time from therapy start to treatment discontinuation or therapy change (next line of therapy – switch or augment), end of enrollment, or death.

PFIZER CONFIDENTIAL

- **Treatment Interruption** – those with gaps in treatment greater than allowable gap but who restart the same medication with no indication of switching or augmentation.
- **Health Care Costs** (inpatient, outpatient, pharmacy, other).
- **Health Care Utilization** (inpatient hospitalizations, ER, outpatient visits).
- **Survival Time and Landmark Survival.** Mean/median survival time and % of population surviving 3, 6, and 12 months will be explored, although regimens are too new for extensive follow-up time. (Note: survival analysis will only be available in the Optum Clininformatics Database).

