The purpose of this initial analysis is to characterize the treatment patterns and treatment duration of adult patients with advanced and metastatic RCC across various real world claims databases (Truven, Optum and Pharmetrics claims). Treatment patterns for these various US population based claims dataset will be assessed for consistency and regimen-specific population differences, as well as assessing feasibility for sub-analyses.

In order to isolate lines of therapy of interest, all medications used for advanced RCC must be considered. Thus, lines of therapy will be performed considering the following RCC medications (see [Table 4](#)):

PFIZER CONFIDENTIAL

Table 4. Medications of Interest

Drug Class	Ingredient	Brand Name	Dosage Form	Mechanism
TKI	Pazopanib	Votrient	Oral	Tyrosine Kinases Inhibitor
TKI	Sunitinib	Sutent	Oral	Multiple receptor tyrosine kinases (RTKs)
TKI	Axitinib	Inlyta	Oral	Kinase inhibitor
TKI	Cabozantinib	Cabometyx/Cometriq	Oral	New Novel TKI
TKI	Sorafenib	Nexavar	Oral	Multikinase inhibitor
TKI	Levantinib	Lenvima	Oral	RTK inhibitor
TKI	Erlotinib	Tarceva	Oral	Epidermal Growth Factor Receptor tyrosine kinase inhibitor
mTOR	Temsirolimus	Torisel	Both oral and IV	Inhibitor of mammalian target of rapamycin
mTOR	Everolimus	Afinitor	Both oral and IV	Mammalian target of rapamycin inhibitor
IO	Ipilimumab	Yervoy	Injection	Human cytotoxic T-lymphocyte antigen 4 (CTLA-4)-blocking antibody
IO	Nivolumab	Opdivo	Injection	Checkpoint monoclonal Antibody PD-1 Inhibitor
IO	Atezolizumab	Tecentriq	Injection	Checkpoint monoclonal Antibody PD-L1 Inhibitor
IO	Durvalumab	Imfinzi	Injection	Checkpoint monoclonal Antibody PD-L1 Inhibitor
IO	Pembrolizumab	Keytruda	Injection	Checkpoint monoclonal Antibody PD-1 Inhibitor
IO	Avelumab	Bavencio	Injection	Checkpoint monoclonal Antibody PD-L1 Inhibitor
IO	Bevacizumab	Avastin	Injection	Recombinant monoclonal antibody VEGF/VEGFR Inhibitor

First-line and subsequent lines (up to 3) of monotherapy and combo-therapy regimens for aRCC patients will be identified and the following metrics will be considered for first-line of therapy:

- Time from first ever metastatic diagnosis to first line regimen;
- Duration of first line therapy;
- Patterns of switching, augmentation and discontinuation;
- Treatment interruptions.

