- **% continuing** – those with no gap in therapy greater than 30 days and who do not begin a new treatment during the study period.
- **% discontinuing** – those with gap in therapy greater than 30 days and who do not begin a new treatment.
- **% with treatment interruption** - those with gap in therapy greater than 30 days but who eventually continue the original treatment (have an additional administration or refill) and do not switch or augment therapy during the study period.
- **% switching** – those with gap in therapy greater than 30 days and who begin a new treatment.
- **% augmenting** – those who begin a new treatment but continue using the original treatment (have an additional administration or refill) and do not have a gap in therapy greater than 30 days of their original treatment.
- **Overall and aRCC Follow-Up Costs:** Total and RCC-specific pharmacy, medical costs from aRCC therapy index through follow-up period (costs summarized as: mean, median costs per patient and costs per patient per month).

PFIZER CONFIDENTIAL

- **Overall and aRCC Follow-Up Utilization:** Total and RCC-specific inpatient, ER, outpatient visits from aRCC therapy index through follow-up period (utilization will be summarized as: mean, median utilization per patient and utilization per patient per month).
- **Overall landmark survival:** Using Optum claims and PanTher data, landmark survival will be described and compared over follow-up time periods (3, 6, 12 months).
- **Mean/Median Survival:** Using Optum claims and PanTher data median survival time will be described and compared over follow-up time periods determined after feasibility assessments of cohorts of interest.

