6.3. Variables

6.3.1. Treatment Pattern Variables

Table 5. Treatment Pattern Variables

Variable	Operational definition
Initial (1L)Treatment Regimen	The first treatment regimen prescribed following a primary and secondary diagnosis of advanced/metastatic disease.
Monotherapy vs Combo therapy	Categorical: Yes/No Combo therapy is defined by a second medication filled on or within 30 days of the original medication and the original medication is filled subsequently. CCI [REDACTED]
Time to FL treatment received	Continuous: days Length of time (days) from the first mRCC diagnosis (first ever secondary malignancy code associated with RCC) to first line therapy prescription.
Treatment discontinuation date (by LoT) – to be used for time to treatment failure (TTF) and time to next line of therapy	Date Treatment discontinuation indicating the end of LOT will be identified as the earliest of: 
For oral therapy: to the run-out date of the last prescription (ie, date of last prescription plus days supply) in the same treatment line.For non-oral therapy: 30 days after the last observed prescription/administration prior to at least a 30 day gap in therapy of all agents included in the first line of therapy.1 day before a new prescription/administration date, whichever occurred earlier.For multiple drug regimens: the above would be triggered by the last prescription/administration in the regimen.Death.End of enrollment.
Days of continuous treatment (by LoT)	Continuous: days The duration of each LOT will be measured from the first prescription or administration of line of therapy medication(s) to the end of the line of therapy, allowing for 30 day allowable gaps in therapy.
Treatment Continuation	Categorical (Y/N) There is no >30 day gap (ie, persistent treatment) for the index medication during follow-up period.

PFIZER CONFIDENTIAL

[REDACTED]

Variable	Operational definition
Treatment Interruption	Categorical (Y/N) At least one instance of >30 day gap (ie, non-persistent treatment) for the index medication during follow-up period or LOT followed by resuming therapy (not mutually exclusive with switch, augment, discontinuation, but a sub-group within LOT).
Interrupted treatment duration	Continuous: days Time from index medication to treatment discontinuation for those within treatment interruptions (>30 day gaps). Represents the time between index and end of last treatment, including any treatment gaps.

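### The discontinuing percentage in 6.1 and Table 7 silently includes every interrupted patient, and interruption itself has two conflicting rules

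*Combined protocol and SAP*

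**What the plan says.** Section 6.1 (Analysis 3) lists five percentages.

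- Discontinuing: "those with gap in therapy greater than 30 days and who do not begin a new treatment". Table 7 repeats this rule.
- Interruption: "those with gap in therapy greater than 30 days but who eventually continue the original treatment", provided they neither switch nor augment during the study period.
- Switching: a gap of more than 30 days together with a new treatment. Table 7 repeats this.
- Augmenting: a new drug is added, the original is refilled or given again, and patients "do not have a gap in therapy greater than 30 days of their original treatment". Table 7 repeats this.
- Continuing: "those with no gap in therapy greater than 30 days and who do not begin a new treatment during the study period".

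The synopsis and Objective 3 (section 5) define interruption as 6.1 does: "gaps in treatment greater than allowable gap but who restart the same medication with no indication of switching or augmentation". Objective 3 gives no rule for switching or continuation.

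Table 5 (6.3.1) defines interruption as a gap of more than 30 days followed by resumption, and adds that it is "not mutually exclusive with switch, augment, discontinuation, but a sub-group within LOT". Its switching row counts a non-index drug that starts either within or after the last persistent index supply plus 30 days. Its continuation row asks only that the index drug has no gap above 30 days. A separate Table 5 row fixes the discontinuation date used for TTF. For non-oral drugs, that row ends the line at a gap of at least 30 days.

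Section 6.7 says no separate SAP is required. Section 6.8 says analyses are programmed from the protocol.

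**The concern.** A patient who pauses for more than 30 days and returns to the same drug would be reported as having discontinued. The error runs one way: resumers can only raise the discontinuing percentage. Analysis 3 presents these outcomes as evidence of unmet need, so an inflated discontinuation figure bears directly on the study's message.

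The interruption percentage is a named Objective 3 outcome, and its value depends on whether 6.1 or Table 5 is programmed. Analysis 1 adds that "Treatment patterns for these various US population based claims dataset will be assessed for consistency", and section 6 says the databases may not be merged, so each is analysed separately. If separate runs follow different sections, a difference in definition could pass for a difference between populations.

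**Working it through.** The plan states no figure to reproduce. The check sets the rules side by side and then uses simple set arithmetic.

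| Outcome | Synopsis / Objective 3 | 6.1 | Table 7 | Table 5 |
|---|---|---|---|---|
| Discontinuing | no percentage defined | gap >30 d, no new drug | same as 6.1 | date rule only |
| Interruption | gap, restart, no switch or augmentation | gap >30 d, restart, no switch or augmentation | not listed | gap >30 d, restart; switch and augmentation allowed |
| Switching | no rule | gap >30 d and new drug | same as 6.1 | non-index drug within or after supply + 30 d |
| Augmenting | no rule | new drug, original refilled, no gap in original | same as 6.1 | new drug while initial therapy continues |
| Continuing | no rule | no gap >30 d, no new drug | not listed | no gap >30 d on index drug |

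**Step 1: interruption lies inside discontinuing.** Under 6.1, a gap plus a new drug is switching. Interruption excludes switchers, so an interrupted patient has a gap and no new drug. That is the whole of the discontinuing rule. The result holds however the gap is measured, because both rules use the same gap condition.

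**Step 2: bound on the overstatement.** Take patients with a gap and no new drug, and let:

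- P = never resumed;
- S = resumed at least once, but not after the last gap;
- R = resumed after the last gap.

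Then 6.1 discontinuing = P + S + R, and 6.1 interruption I = S + R. Discontinuing without resumption = P + S. The fall is (P + S + R) − (P + S) = R, and R ≤ I.

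**Step 3: what the five percentages add up to.** Assume gaps are measured on the index regimen, which 6.1 says only for augmenting. Let U be patients who start a new drug with no index gap above 30 days and no later index refill. They meet none of the five 6.1 rules. Continuing + discontinuing + switching + augmenting + U = 100%. Adding I, which is already inside discontinuing, gives a five-category sum of 100% + I − U.

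**Step 4: illustration, with assumed rates.** The documents give none. Suppose 20% stop and do not resume, and nobody resumes and later stops (S = 0, so I = R).

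| Interrupted (assumed) | 6.1 discontinuing | Share of these who resumed |
|---|---|---|
| 5% | 20 + 5 = 25% | 5/25 = 20% |
| 10% | 20 + 10 = 30% | 10/30 = 33% |
| 20% | 20 + 20 = 40% | 20/40 = 50% |
| 30% | 20 + 30 = 50% | 30/50 = 60% |

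**Step 5: 6.1 against Table 5.**

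- Interruption differs for anyone who has a gap, resumes, and also starts a new drug: 6.1 no, Table 5 yes.
- Continuation differs for augmenters: 6.1 no, Table 5 yes.
- Switching can differ for the U group in step 3: no label in 6.1, a switcher on the natural reading of Table 5.

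**Step 6: precedence.** The reference from 6.1 to 6.3.1 concerns oral versus injectable rules for time treated. Section 6.8 points to the protocol as a whole. Neither ranks 6.1, Table 5 and Table 7.

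**The case against.** The strongest reply is that the overlap is intended. Table 5 says interruption can coexist with discontinuation. Its discontinuation-date row ends a non-oral line at a gap of at least 30 days even if the drug is later resumed. On that reading, 6.1 discontinuing matches the TTF rule for injectables, and only a footnote is missing.

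Part of this stands. For injectables, counting a resumer as discontinued does agree with the TTF date rule, so any repair must address that row. No passage says that the five percentages are exclusive or must total 100%, so a reader should not infer from step 3 that the plan breaks a rule of its own. It shows undeclared overlap.

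It does not dispose of the point. The Table 5 note describes Table 5's own flag, which contradicts 6.1 on switching and augmentation, so it cannot serve as the explanation of 6.1. Neither 6.1 nor Table 7 tells the reader that resumers are included.

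The secondary conflicts are weaker. Table 5 switching refers to the last persistent index prescription, which might be read as implying a later gap. Table 5 augmentation requires the initial therapy to continue, and Table 5 defines continuation as no gap above 30 days, so a firm contradiction on augmenting is not established. Table 5 continuation already describes itself as index-drug persistence, so that conflict is largely one of labels.

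**Conclusion.** The concern holds in two main parts. First, discontinuing in 6.1 and Table 7 contains all of 6.1 interruption and so overstates discontinuation without saying so. Second, interruption has one rule in the synopsis, Objective 3 and 6.1, and another in Table 5, with nothing to choose between them. The switching and continuation differences are real but secondary, and partly rest on loose wording.

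The overstatement is R, which is at most the 6.1 interruption percentage. Its actual size cannot be derived from the documents, and the step 4 rates are assumptions. Step 1 rests on wording alone. Step 3 also needs index-regimen gaps.

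Three stronger conclusions might be inferred, and the documents do not support them. One is that Objective 3 also conflicts with Table 5 on switching and continuation; it defines interruption only. Another is that a stated share of patients is misclassified; no rates are given. The third is that TTF is wrong for the same reason; it has its own date rule. For a descriptive study this should be settled before programming, but it does not undermine the design.

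**What to change.** 1. In 6.1 and Table 7, split discontinuing into two lines, both requiring a gap above 30 days and no new treatment: original not resumed after the last gap by end of follow-up, and original resumed.
2. Keep the Objective 3 and 6.1 interruption definition unchanged as the reported outcome. Rename the Table 5 version as any interruption, which may overlap switching or augmentation. State that a patient who resumed and later stopped counts in both interruption and discontinuing.
3. State that gaps are measured on the index regimen. Use the 6.1 and Table 7 switching and augmenting rules in Table 5 as well. Rename Table 5 continuation as index-drug persistence. Report separately any patient who starts a new drug but meets no 6.1 category.
4. Reconcile these labels with the Table 5 discontinuation-date row. State that TTF may count a gap as an event for a patient who later resumes, so the TTF event count and the not-resumed percentage can differ.

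Cost: wording changes and one classification routine, with no new data. The not-resumed label depends on length of follow-up, since a patient may be not resumed at 3 months and resumed by 12. It should therefore be reported separately within the 3-, 6- and 12-month cohorts.

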6.2. Setting

Anonymized patient data available in US administrative research database will be used for this study. This study will utilize various databases including the Truven Marketscan Commercial, Optum Clininformatics DOD (includes death data from the Social Security Death Masterfile), and PharMetrics Claims data all representing patients enrolled in US commercial health plans, Medicare or Medicaid. Plan enrollment information is available with these data. The Optum PanTher database will also be used as it represents patients with both Optum claims data and Humedica EMR data, which includes a large database of terms extracted from EMR notes fields. Sub-analysis specified will use wider structured data elements, such as reasons for treatment failure, which may be extracted from the EMR notes fields.

[figure not shown]
Inclusion and exclusion criteria are detailed below in [Sections 6.2.1](#) and [6.2.2](#). All patients meeting eligibility requirements will be included in the analyses. The resulting population is expected to be representative of patients with the types of insurance coverage available in the source databases. The databases listed in [Section 6.4](#) will be evaluated. This protocol may also be amended to include additional databases over time.

6.2.1. Inclusion Criteria

Subjects will be selected irrespective of their survival status. Patients must meet all of the following inclusion criteria to be eligible for inclusion in the study:

- **Index date:** The first prescription or administration of one of the medications indicated for advanced RCC recorded in the database between April 2018-March 31, 2019, among those with no aRCC treatment in their history.
- Age 18 years or older in the year of the index first line therapy prescription.
- 2 or more RCC diagnoses (ICD-9: 189.0; ICD-10: C64.1, C64.2, C64.9) at least 30 days apart, in the 1 year prior to the index date until 30 days post index date.

PFIZER CONFIDENTIAL

- 2 or more code for secondary malignancy codes indicating possible diagnoses for metastatic disease at least 30 days apart, in the 1 year prior to the index date until 30 days post index date. (ICD-9: xx-199.xx; ICD-10: C77-C79, except ICD9: 198.0 Secondary malignant neoplasm of the kidney and ICD10: C79.0 Secondary malignant neoplasm of the kidney and renal pelvis).
 - CCI [REDACTED]
- Continuous enrollment from 12 months prior to the index date. Patients will be required to have continuous enrollment from their index date until the end of the available data. This will allow for sub-analysis of cohorts with 3 months, 6 months and 12 months of available data.

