6.1. Study Design

Patients receiving aRCC treatment (see [Table 4](#)), between April 2018 and the present, who have no prior aRCC treatment in their claims history will be identified for this study. The index date for each analysis will be defined as the date of initiation of the aRCC treatment. Patients must have at least 2 RCC diagnoses at least 30 days apart to be included. Patients must also have 2 secondary malignancy ICD9 or ICD10 codes (often used in claims data to suggest cancer metastases) at least 30 days apart in the 12 months pre and one month post index aRCC treatment. [CCI](#)

Various algorithms and temporal relationships between the secondary malignancy codes, RCC diagnosis codes and other cancer codes were explored toward developing the criteria for metastatic advanced RCC for this study.

Study will require a minimum of 12 months of enrollment prior to the index date. Feasibility was assessed for various lengths of continuous enrollment criteria (3, 6 and 12 months post index date) toward understanding sample sizes available for analysis and follow-up periods. Study outcomes will be assessed for three patient cohorts (3, 6 and 12 month cohorts) according to their available months of continuous enrollment.

PFIZER CONFIDENTIAL

First line therapy cohorts will first be presented for all patients regardless of follow-up time available. Baseline characteristics, costs and utilization will be measured over the 6 months prior to the index date. Duration of therapy and utilization analysis will require at least 6 months of post-index enrollment, with sub-analysis preformed on the cohorts with 3-months and 12-months of post-index enrollment. Utilization and cost will be performed per-utilizer-per-month (PUPM), and then separately for each of the cohorts with 3-month, 6-month and 12-months of post-index enrollment.

The analysis will focus on, but is not limited to, the following regimens:

- a. **Combo IO:** nivolumab combined with ipilimumab;
- b. **Monotherapy TKI:** sunitinib, cabozantinib, and pazopanib;
- c. **Combo TKI + IO:** avelumab in combination with axitinib, pembrolizumab in combination with axitinib;
- d. **Other:** all others regimens.

PFIZER CONFIDENTIAL

[figure not shown]
[figure not shown]
[figure not shown]

Figure 1: Cohort Identification

Analysis 1. Treatment Patterns and Duration

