Treated Period Follow-Up. Patients will be followed over the period treated with advanced RCC therapy. Time treated will be defined as the time from the index date to the date of the end of the last advanced metastatic RCC prescription (end of supply for orals/administration date plus 30 days for injectables), end of enrollment, end of follow up, or death (see more specifics on oral versus injectable rules in [6.3.1 Variables](#) section of this protocol).

Analysis 2. Describe various treated populations of interest by demographics, clinical characteristics, as well as cost and utilization

Describe the demographics and other baseline characteristics of the first-line treated cohorts of interest identified in the treatment patterns analysis (Analysis 1) for RCC patient as follows:

Baseline Characteristics (see [6.3.2 Baseline Characteristics](#)):

- Age at index;
- Gender;
- Race;
- Region;

PFIZER CONFIDENTIAL

- Payor;
- Clinical characteristics: Quan-Charlson Comorbidity Index (CCI) scores and baseline comorbidities;
- Prior treatment (6 months prior) - nephrectomy, radiation/ablation, interferon, high-dose interleukin-2, other anti-neoplastic medications;
- Secondary malignancy locations (6 months prior);
- Baseline costs of care (6 months prior);
- Baseline health care resource utilization (6 months prior).

Analysis 3: Evaluate the key outcomes of interest for advanced RCC therapy regimens toward demonstrating existing unmet needs in RCC given currently available therapies (eg, ipilimumab/nivolumab).

Treatment duration, discontinuation, interruption, switching and therapy augmentation will be presented, as will the burden of disease costs and health care utilization. Survival will also be explored, although regimens are too new for extensive follow-up time.

Overall Outcomes Study Period. For the outcomes analysis, follow-up will be defined as the time from the index date to the end of specified follow up period of 6 months, end of enrollment, or death. Follow-up may vary given sample sizes of study population, with by subanalysis using 1-year or 2-years of follow-up time from study index date for certain sub-populations.

Outcomes include:

- **Time to Treatment Failure (TTF)** – First line time to treatment failure (TTF) is defined as the time from first-line therapy start to treatment discontinuation for any reason, including switched, augmented therapy, end of enrollment, death.

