6.2.2. Exclusion Criteria

Patients meeting any of the following criteria will not be included in the study:

- Received advanced treatment prior to the study index date.
- Prescription records with negative days of supply will be excluded from all the analyses except in cost variable calculation. The day of supply for claims with missing or 0 days will be imputed.
- Only one RCC diagnosis in the 12 months prior or one month post index date.
- Patients with data for analysis (<3 months post index date).

PFIZER CONFIDENTIAL

[REDACTED]

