6.3.3. Outcomes Variables

Table 7. Outcomes Variables

Variable	Operational definition
Days to Treatment Failure (TTF)	Time to treatment failure (TTF) is defined as the time from therapy start to treatment discontinuation for any reason, including switched, augmented therapy, end of enrollment, death.
Discontinuation	% discontinuing – those with gap in therapy greater than 30 days and who do not begin a new treatment.
Switching	% switching – those with gap in therapy greater than 30 days and who begin a new treatment.
Augmentation	% augmenting – those who begin a new treatment but continue using the original treatment (have an additional administration or refill) and do not have a gap in therapy greater than 30 days of their original treatment.
% Survived 3,6, 12 months	Mean/Median Survival Time (Days): Survival time will be described over 3,6, 12 months given follow-up time available in the data. Overall survival is defined as the length of time from index date of RCC diagnosis to patient death (or index date associated with FL Tx?) or end of available data for with no death indication. Overall landmark survival: described and compared over follow-up time periods (3,6, 12 months). Percentage of patients alive at 3,6, 12 months.
Overall Survival Time	Continuous: days Overall survival is defined as the length of time from index date of RCC diagnosis to patient death (or index date associated with FL Tx?)

PFIZER CONFIDENTIAL

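### Diagnosis-code entry rules that can be completed up to 30 days after treatment start build guaranteed early survival into the survival analysis for part of the cohort

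*Combined protocol and SAP*

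**What the plan says.** Section 6.2.1 sets the index date at "The first prescription or administration of one of the medications indicated for advanced RCC recorded in the database between April 2018-March 31, 2019", among patients with no earlier aRCC treatment. It then imposes two code rules with the same spacing and window. One needs two RCC diagnoses. The other needs "2 or more code for secondary malignancy codes indicating possible diagnoses for metastatic disease at least 30 days apart". Each pair must fall within the window described as "at least 30 days apart, in the 1 year prior to the index date until 30 days post index date".

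Section 6.1 repeats the secondary-malignancy rule ("at least 30 days apart in the 12 months pre and one month post index aRCC treatment"). Section 6.2.2 mirrors the RCC rule by excluding patients with "Only one RCC diagnosis in the 12 months prior or one month post index date".

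Section 6.2.1 opens with this principle: "Subjects will be selected irrespective of their survival status".

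On outcomes, Section 6.1 defines first-line TTF as "the time from first-line therapy start to treatment discontinuation for any reason, including switched, augmented therapy, end of enrollment, death". Table 7 (Section 6.3.3) asks for "Percentage of patients alive at 3,6, 12 months". Section 6.7 plans Kaplan-Meier curves for duration of therapy and survival. It mentions no delayed entry, no later start of follow-up and no sensitivity analysis on how patients qualified.

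**The concern.** Part of the qualifying window lies after time zero. Anyone who completes a code pair only after index has, by definition, lived and stayed in care until that code. A patient with the same history who dies first fails the rule and is never counted. The time between index and the completing code is then follow-up in which a death could not have been observed.

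The patients exposed are those treated within a month of their first RCC code or first secondary-malignancy code, that is, rapidly treated disease. The 3-month landmark is at stake most, and the later landmarks less. Section 6.1 says survival will be compared as well as described, so an uneven spread of such patients across regimens would matter.

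**Working it through.** The plan states no survival figure and no sample size to reproduce, so the check has two parts.

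**1. Date arithmetic, from the protocol alone.** Let the first code of a pair fall d days before index. The second must come at least 30 days later, so no earlier than day 30-d. The window closes at day 30.

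| d (days before index) | Earliest completing day | Days in which the second code can fall |
|---|---|---|
| 0 | 30 | 1 |
| 7 | 23 | 8 |
| 14 | 16 | 15 |
| 21 | 9 | 22 |
| 29 | 1 | 30 |
| 30 or more | 0 (none forced) | not applicable |

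The minimum guaranteed survival is max(0, 30-d). Its mean over d = 0 to 29 is 15.5 days. Patients with d of 30 or more whose second code happens to come after index are also selected on survival, but the rule does not force this.

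**2. Size, under stated assumptions.** The documents give neither 12-month survival (S12) nor the share f of patients with d below 30. Assume constant hazard h = -ln(S12)/365.25, d uniform on 0 to 29, and early deaths otherwise retained. For t beyond 30 days,

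observed S(t) = S(t) / [(1-f) + f·m], where m is the mean of exp(-h·g) over g = 1 to 30.

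- S12 = 60%: h = 0.5108/365.25 = 0.001399, m = 0.9786, S(91.3 days) = 0.8801. With f = 30%, the denominator is 0.7 + 0.3 × 0.9786 = 0.9936 and observed survival is 0.886, or +0.6 points. With f = 100% it is 0.8801/0.9786 = 0.899, or +1.9 points.
- S12 = 80%: h = 0.2231/365.25 = 0.000611, m = 0.9906, S(91.3 days) = 0.946. With f = 30%, the denominator is 0.9972 and observed survival is 0.948, or +0.3 points.

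| Assumed S12 | Assumed f | Inflation at 3 / 6 / 12 months (points) |
|---|---|---|
| 60% | 10% | 0.2 / 0.2 / 0.1 |
| 60% | 30% | 0.6 / 0.5 / 0.4 |
| 60% | 100% | 1.9 / 1.7 / 1.3 |
| 80% | 30% | 0.3 / 0.3 / 0.2 |
| 80% | 100% | 0.9 / 0.8 / 0.8 |
| 90% | 10% | under 0.1 throughout |

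Front-loaded deaths enlarge the effect. If 10% die within 30 days, spread evenly, and f = 50%, the excluded share is 0.5 × 0.10 × 15.5/30 = 0.0258. Every landmark survival figure then rises by 1/(1-0.0258) - 1 = 2.65% in relative terms.

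**Ceiling for a single patient type (d = 0).** Use 90 days and a 365-day year. At S12 = 60%, true 3-month survival is exp(-0.5108 × 90/365) = 88.2%. Given survival to day 30, it is exp(-0.5108 × 60/365) = 91.9%. At S12 = 80% the pair is 94.6% and 96.4%. Mortality falls from 11.8% to 8.1%, or from 5.4% to 3.6%, which is about one third.

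**The case against.** The strongest reply is that other conditions may absorb the effect. Section 6.2.1 requires continuous enrollment from index to the end of the data. Section 6.2.2 has an incompletely worded exclusion about less than 3 months after index. Section 6.1 requires 6 months of post-index enrollment for duration of therapy. If death counts as failing these, 3-month survival is 100% by construction, the code rules add nothing there, and delayed entry changes nothing. This stands. The code-rule bias shows only where early deaths are kept, as the survival-status principle in Section 6.2.1 implies, and as does the statement in Section 6.1 that first-line cohorts are first presented whatever their follow-up. Exempting deaths from the enrollment conditions would not cure it, because an early death still fails the code rule.

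The survival origin is also unsettled. Section 6.1 and Section 6.2.1 use treatment start, Table 6 defines index as first RCC diagnosis, and Table 7 leaves the choice as an open question. That stands too, but a diagnosis origin would lengthen the guaranteed time, since patients must also survive to treatment.

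A sub-item under the secondary-malignancy rule is blacked out, so that rule is not fully visible. None is blacked out under the RCC rule, which produces the problem on its own.

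Three stronger readings are tempting, and the documents do not support them:

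- A reader might infer that the cohort's 3-month mortality is understated by a third. That is the d = 0 ceiling, and such a patient needs a code exactly on day 30.
- A reader might infer that all early TTF events are blocked. Switching, augmentation and oral run-out can still end TTF before the completing code.
- A reader might infer that regimen comparisons are distorted. That needs the affected share or the early hazard to differ by regimen, and the documents report neither.

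**Conclusion.** The mechanism follows from the protocol's own dates, contradicts its selection principle, and is not corrected by the planned Kaplan-Meier analysis. Each affected patient carries 1 to 30 days of guaranteed survival, provided that survival runs from treatment start and early deaths are otherwise retained.

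The cohort-level effect is probably small: about 0.3 to 0.6 points at 3 months if 30% are affected and 12-month survival is 80% or 60%, and 1.9 points if all are affected at 60%. These figures rest on assumed survival, assumed shares, constant hazard and uniform d.

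For TTF, the rule suppresses only early failure through death or end of enrollment. Table 5 dates non-oral discontinuation 30 days after the last administration, so for those drugs death is one of the few events that could end TTF within the first month. The point merits correction because the remedy is cheap, but it is tied to the enrollment and time-origin conflicts.

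**What to change.** Keep the entry rules and the sample, and make these changes in order:

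1. Settle treatment start as the survival origin, and align Table 6 and Table 7 with it.
2. Reconcile the post-index enrollment conditions in Sections 6.1, 6.2.1 and 6.2.2 so that a death does not exclude a patient. Without this step the rest has no effect on 3-month survival.
3. In Section 6.7, enter each patient into the survival Kaplan-Meier risk set at the later of index and the date on which the last of the two code rules is completed. Read the 3-, 6- and 12-month percentages from that curve.
4. Do the same for TTF, and report how many patients fail before their entry date.
5. Report, by regimen, the share who qualify only after index.
6. Add a sensitivity analysis limited to patients with both code pairs complete on or before index. State that it removes rapidly treated patients and so changes the population.

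The cost is one entry-date variable built from dates already extracted, and one extra run. Risk sets in the first 30 days will be smaller, reported early survival will be slightly lower, and the earliest part of the curve will rest mainly on patients who had already qualified by index.
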